2.5 Pharmacokinetics in humans

Twelve hundred milligrams of boswellia resulted in plasma concentrations of 10-32 µl M of 11-keto-β-boswellia acid and 18-20 µl M acetyl-11-keto-β-boswellic acid, measured 2-3 hours following administration (54).

A small pilot bioavailability study after administration of the Boswellia serrata soft gelatine capsules BOSWELAN (Medeon GmbH) in six healthy subjects resulted in a maximal peak concentration of 180.9 ± 57.59 ng/ml for KBA and of 34.8 ± 19.19 ng/ml for AKBA within the first two hours after administration with a half-time of 2.45 ± 0.44 hours for KBA and of 1.14 ± 0.24 hours for AKBA.

Food effect

In a recently completed Phase I, open, randomised, cross-over pharmacokinetics study plasma levels of KBA and AKBA after a single oral morning dose of 800 mg Boswelan after either a standardized breakfast or after an overnight fasting period (fasting) were assessed. Plasma levels were about twofold higher under "with meal" conditions. From a different study about 200 fold higher plasma concentrations were achieved by βBA and AβBA, compared to KBA.

2.5.1 Clinical Studies Assessing the Safety, Tolerance and Efficacy

BAs are generally believed to be safe. BA-containing extracts have already been used in several randomised placebo-controlled clinical phase II- and -III studies. BAs have shown beneficial effects in rheumatoid arthritis, asthma bronchiale and osteoarthritis (evidence level B and C). BAs were well tolerated (55) based on altogether 7 reported adverse events (3 cases of local skin reaction, 1 case of diarrhea, 1 case of gastral intolerability) in 233 patients who received BA extracts. Similarly, in a recent review about placebo-controlled studies with BAs in patients suffering from autoimmune diseases (i.e. asthma, rheumatoid arthritis, Crohn's and others) adverse events were described in max. 5% of BA-treated patients, mostly presenting as gastrointestinal intolerability, i.e. nausea, acid reflux, mild gastrointestinal upset, diarrhoea (56). No allergic or hypersensitivity to BAs have been reported in the available

literature.

A double-blind placebo-controlled Phase II study with BOSWELAN in inflammatory bowel disease has recently been conducted. In the recent interim-analysis of 76 patients (2 groups of 38 patients each with BOSWELAN vs. placebo), no significant no serious adverse events were reported.

With respect to the clinical use of BAs, more than 500 patients (with different inflammatory, mainly autoimmune diseases) have been treated, and no serious adverse events have been reported from any of the clinical trials (56).

High doses of frankincense extracts up to 4800mg/d have been well tolerated in a couple of well documented cases and studies in cancer patients, including children (45,46,54,55).

In addition to pharmacokinetic and animal toxicity data BA extracts (BOSWELAN) show an excellent safety profile even up to doses of 3600mg/d (2400mg/d) (BOSWELAN, see Investigator's brochure). Regulatory permission based on the toxicology data for the standardized frankincense extract BOSWELAN has already been granted from the BfArM for the above mentioned Phase II study in Crohn's disease. Data concerning the treatment of MS with BA are currently not available, and approval of BOSWELAN or any other frankincense extract for the treatment of MS has not yet been granted, but is expected to be granted without any major anticipated problems.

The most common complaints in trial have been skin irritations and dermatitis (55-57). In 38 patients with Crohn's disease, treated for one year with 800 mg t.i.d., no serious adverse events were observed.

For any further information on toxicology, preclinical studies, and pharmacokinetics please refer to the Expert Safety Review on *Boswellia serrata* Extracts (7th March 2011) and the CMC Review for Boswelan[®] (14th March 2011).

2.5.2 Dose justification

In conclusion from the abovementioned studies we deduce as minimum effective dose 800mg t.i.d., which is sufficient to induce plasma levels of AKBA *in vivo* that have previously been shown to inhibit Cathepsin G *in vitro*. The other two enzymes that are relevant to be inhibited by boswellic acids in the context of MS, namely 5-LO and mPGE1 require higher doses between 1-10µM of AKBA for inhibition, and consequently higher doses of BA extracts are probably needed to achieve these effects. 4800 mg/d (1600 mg t.i.d.) is the highest dose that we are planning to administer in this study because frankincense extracts have been reported to be safe and well tolerated up to this dose (45,46,54,55) and due to their higher efficacy that has been shown in studies of cerebral malignancies.

The minimal no observable adverse effect level (NOAEL) as documented in the toxicology studies translates to the following human equivalent doses (HEDs):

Table 1: Translation of minimal NOAEL doses from rat / dog to man

Species	NOAEL/LTD mg/kg	mg/kg	mg/m2
Rat	300	300	1770

	600	600	3540
	900 (LTD)	900	5310
Man/Rat		6.8	253
		13.7	506
		20.5	759
Dog	100	100	2000
	300 (LTD)	300	6000
Man/Dog		27	1000
		81	3000

Source: Guidance for Industry. Estimating the Maximum safe Starting Dose in Initial Clinical Trials for Therapeutics in Healthy Adult Volunteers. US CDER, July 2005, Pharmacology and Toxicology

The doses used with *Boswellia serrata* extract formulations in man to date range from approximately 1200 mg to 4800 mg per day divided over 3 daily doses. Clinical experience indicates that, dependent on the indication, optimal daily doses range between 3600 mg and 4800 mg/day in the acute phase or during initiation of treatment (below also referred to as higher, previously applied dose range) and between 1200 mg and 2400 mg/day (below also referred to as intermediate dose range) during maintenance therapy.

Therefore, the highest applied daily human dose (3600 mg – 4800 mg, approx. 70 kg b.w.) is between 51,4 - 68,5 mg/kg and 17,1 - 34,3 mg/kg for the maintenance doses based on the conversion standards as provided by the FDAs “Guidance for Industry. Estimating the Maximum safe Starting Dose in Initial Clinical Trials for Therapeutics in Healthy Adult Volunteers”, US CDER, July 2005, Pharmacology and Toxicology.

These daily doses, which have already been applied in man, are considerably above the NOAEL and even the lowest toxic dose (LTD) in the rat, above the NOAEL in the dog, but below the LTD in dog in repeated dose chronic toxicity. The rat appears to be the most sensitive model in repeated dose chronic toxicity. However, in safety pharmacology studies in the rat single doses up to 2700 mg were largely unproblematic, while earlier toxicological studies (1) demonstrated a cloudy swelling of liver and kidneys with doses up to 10 times the human dose. In chronic toxicology studies in rats the LTD was mainly determined by a significant increase of liver weight. Significant biochemical, hematological and histopathological changes were only encountered at high doses. In the dog toxicity was limited to the liver without any further changes, including histopathology, in any other system at any dose level

At the initial 900 mg/kg dose in dogs a moderate increase in total bilirubin, total cholesterol and alkaline phosphatase (AP) was observed. None of these findings were significant compared to control. While bilirubin was normalized, cholesterol and AP dropped by 50%-65% upon dose reduction to 300 mg/kg, the dose that was originally defined as the LTD for this group, with complete reversibility during recovery. Therefore we deem it appropriate to ask, whether a conversion to HED based on guideline standards is meaningful for extract compositions, in particular *Boswellia serrata*. The guideline standards apply in principle to single molecules with a defined pharmacological activity.

Boswellia serrata resin extracts basically contain the following substances: essential oils (more than 80 different compounds including mono-, di- and triterpenes), resin acids, ether-insoluble components (neutral and acidic

polysaccharides) and ether-soluble compounds (higher terpenes and boswellic acids; 56, 57). Boswellic acids have been identified as the main active moieties contained in *Boswellia seirata* oleogum resin.

Besides the possibility that the various active moieties contained in the extract, the boswellic acids in particular, may not yield the same bioavailability, in different species. In consequence, this may lead to differing pharmacokinetic, and, as a consequence, probably also pharmacodynamic profiles. Generally, it has to be considered that such an extract contains large quantities of lipophilic components, both pharmacologically active and inactive, which may be preferentially stored in the liver following first-pass (and subsequently eventually in e.g. kidney and bone marrow).

Therefore, the initial changes encountered at the LTD levels in rat and dog may be related to the volume i.e. the relative weight of lipophilic material applied rather than the dose intensity of the active moieties contained therein.

If the relative weight of the doses of native extract applied is considered, the upper limit of the dose range based on previously applied doses and projected in man of 52-69 mg/kg compared with the NOAEL and LTD in rat provides a "therapeutic window" ratio of at least 8, respectively 13.

Compared with the NOAEL and LTD in dogs, these ratios are at least 2 and 4 respectively. The ratios increase considerably if the intermediate dose range is considered. However, the safety margin is effectively much wider as the daily dose in man is split into 3 doses/day.

From a toxicological point of view, *Boswellia serrata* extract appears to possess at least a margin of safety as wide as e.g. mesalazine, if not even wider. Evidence of renal papillary necrosis was found for mesalazine in dogs already at 60 mg/kg b.w./day treated for 12 months (56). Mesalazine is used at a higher therapeutic dose of approx. 64 mg/kg b.w./day in man.

In conclusion, based on standard conversion rates, the previously applied and projected doses in man provide a narrow therapeutic window of safety compared to the NOAEL and LTD established in rats and dogs. In contrast a comparison based on relative weight of native extract of *Boswellia serrata* that is given provides a considerable safety margin. On the basis of the above consideration and the existing data from application of *Boswellia serrata* extracts at higher dose levels in humans we believe that a carefully conducted dose escalation from intermediate to higher dose levels is justified and safe.

3. Objectives and Outcome Measures

3.1 Primary Objective

The primary objective of this study is to determine the safety and tolerability of BOSWELAN in subjects with CIS or RR multiple sclerosis using side effect monitoring MRI (primary MRI safety parameter: mean total number of Gd-enhancing lesions), clinical, and laboratory measures.

3.2 Secondary Objective

The secondary objective of this study is to determine the effect of BOSWELAN therapy on disease activity in CIS or RR multiple sclerosis as measured by MRI

activity. In addition, the effect of BOSWELAN on immunological function will be assessed.

The primary efficacy outcome measure of this study will be the mean total number and the volume of Gd-enhancing lesions based on a comparison of 4 baseline MRIs and 4 treatment MRIs (months 5-8) in patients of this study who tolerated a dose of at least 800 mg t.i.d.

Secondary outcome measures will be:

1. Number of new active lesions (new Gd-enhancing lesions plus new non-enhancing or enlarging T2 lesions). Number of persisting Gd-enhancing lesions. Number of new Gd-enhancing lesions evolving into persistent T1 hypointense lesions. T2 lesion volume (fast spin echo sequence), T1 hypointense lesion volume, Number of persisting T1 lesions, Magnetization Transfer Ratio (MTR), brain parenchymal fraction as measure of atrophy
2. Relapse rate

Tertiary outcome measures will be:

1. Magnetic resonance spectroscopy (MRS). Multivoxel magnetic resonance spectroscopy will be performed once during the baseline and twice during the treatment phase (months 4 and 8) in three patients (those with the highest EDSS).
2. Expanded disability status scale (EDSS), SCRIPPS neurological rating scale (SNRS), MS functional composite (MSFC) consisting of 9-HP-test (Nine-Hole-Peg Test), timed 25 foot walk, paced auditory serial addition test (PASAT), and in addition a depression scale (Hospital Anxiety and Depression Scale) and a fatigue scale (Fatigue severity scale according to Flachenecker), Hamburg Relapse Assessment Scale (HARAS).

Immunological measures:

A number of immunological measures will be studied to determine the in vivo immunomodulatory effect, in particular the influence on T helper 1 (Th1) and Th2 cytokines,

Biomarker assessments:

Cathepsin G and mPEGS-1 serum levels will be analyzed at every visit starting from baseline (month 0).

4. Study Outline

Months -3 - 0	Month 1	Month 2	Months 3-8	Months 9-12
Baseline MRI Lesion frequency of 0.5 or greater	Dose escalation to treatment dose Monthly MRI	Stabilization of dose Monthly MRI	Primary treatment phase Monthly MRI Assessment of individual treatment effect	Follow up of patients until Month 12 and MRI; optional for patients: washout or treatment continuation

5. Study Population

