Dosing will be discontinued in patients showing an increase in total Gd-enhancing lesions beyond 6 standard deviations of the mean lesion frequency during baseline plus 10 lesions. The maximum lesion number allowed during treatment will be 40 Gd-enhancing lesions. The upper margin (40 Gd-enhancing lesions) stems from a systematic review of the numbers and distribution of contrast-enhancing lesions derived from the placebo cohorts of pivotal phase III trials, which was performed by the Sylvia Lawry Center for MS Research ([name] and colleagues). Furthermore, if in the opinion of the investigators there is a change in appearance of enhancing lesions inconsistent with the patient's previous MRIs, e.g. change in average lesion size from small to substantially larger lesions, dosing will be discontinued.

Two clinical safety criteria will also be used as stopping criteria:

Clinical criterion 1- relapses: Two or more confirmed relapses/exacerbations (see section 7.3.2 for definition of relapse/exacerbation) or clinical criterion 2 - progression: Worsening of two or more points on the EDSS scale during the treatment phase, compared to baseline post treatment, confirmed and consistent through three monthly visits.

If dosing had to be discontinued in five patients because of MRI parameters or in more than 1 of the first 4 participants, more than 2 of the first 8 participants, and 3 or more participants in the entire group because of clinical parameters the study will be placed on clinical hold, i.e. treatment with BOSWELAN of all patients already in the study will be discontinued and no additional patients will be recruited until the data from the trial has been reviewed by the safety committee.

Side effect monitoring, blood biochemistry (especially liver enzyme levels), as well as neurological and other clinical parameters will be used to further assess safety.

Efficacy

Parameters:

Primary outcome measure

- Number and volume of total Gd-enhancing lesions

Secondary outcome measures

- Number of persisting Gd-enhancing lesions
- Number of new active lesions (new Gd-enhancing lesions +new or enlarging non-enhancing T2 lesions)
- Number of new Gd-enhancing lesions evolving into persistent hypointense lesions
- T2 lesion volume
- T1 hypointense lesion volume
- Number of persisting T1 lesions
- Brain atrophy (brain parenchymal fraction)
- Magnetization Transfer Ratio (MTR)
- Relapse rate

Tertiary outcome measures

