- MRS (multi-voxel magnetic resonance spectroscopy)
- Neurological measures: Expanded disability status scale (EDSS), SCRIPPS neurological rating scale (SNRS), MS functional composite (MSFC) consisting of 9-HP-test (Nine-Hole-Peg Test), timed 25 foot walk, paced auditory serial addition test (PASAT), Depression scale (Hospital Anxiety and Depression Scale) and a fatigue scale (Fatigue severity scale according to Flachenecker et al.), Hamburg Relapse Assessment Scale (HARAS)
- Immunological parameters
- Biomarker assessment (Cathepsin G activity and PGE₂ levels)

Patient selection: Subjects with clinically isolated syndrome (CIS) fulfilling MRI inclusion criteria (see below) or clinically definite relapsing remitting multiple sclerosis (RRMS) in an active inflammatory phase who either failed standard treatment by clinical measures or were not eligible for any of the standard treatments (e.g. interferon beta, glatiramer acetate) or, after consultation with an independent neurologist, elected not to start or to continue with any of these treatments. Subjects will be enrolled following completion of all pre-screening procedures. After enrollment, subjects will undergo baseline Gd-enhanced MRIs at 4-week intervals prior to the first dose of study drug.

Statistical Plan: Evaluable populations

The primary outcome in the treatment phase (Stage 3) will first compare mean Gd-enhancing lesion number occurring during the 4 month baseline to mean Gd-enhancing lesion number occurring months 5, 6, 7, 8 on treatment in patients treated with a dose of at least 800 mg t.i.d.

A secondary analysis will compare mean Gd-enhancing lesion number occurring over the 4 months of baseline to that occurring during all treatment months on treatment.

Sample size

Based on analyses of a natural history cohort studied with monthly MRIs for a minimum of one year, a baseline-to-treatment designed trial incorporating 4 baseline MRIs and 4 treatment MRIs will require 30 patients to detect a 40% reduction in Gd-enhancing lesions with an alpha of 0.05 (one-sided).

2. Introduction and Study Rationale

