The individual well tolerated dose from Stage 1 will be used for each patient in a subsequent 4-week stabilization phase during which the dose will be observed for continuous safety and toleration. Afterwards this individual maximal well tolerated dose will be used in Stage 3 of the study for further 6 months. Patients not tolerating the minimum dose of 800mg t.i.d. will be excluded from the study.

Stage 3

In Stage 3 of the study, patients will be treated with their individual well tolerated dose of BOSWELAN as assessed in Stage 2 subsequently for six months. The minimum dose for patients to be considered evaluable in the primary statistical analysis will be 800mg t.i.d..

The primary outcome will assess the change in mean Gd-enhancing lesion number from the baseline to that observed over months 5, 6, 7 and 8 since a delay in treatment effect is expected. In addition to MRI evaluation, patients will have monthly neurological evaluations and immunological assessment.

Stage 4

After completing Stage 3 patients are offered to continue their BOSWELAN dose for 4 months or to stop drug intake after month 8. In any case patients are seen for clinical and MRI-follow-up at month 12 at the study center.

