13.1 Sample Size Considerations

Based on analyses of a natural history cohort studied with monthly MRIs for a minimum of one year, a baseline to treatment designed trial incorporating 4 baseline MRIs and 4 treatment MRIs will require 12 patients to detect a 60% reduction in Gd-enhancing lesions with an alpha of 0.05 (one-sided). Regarding BA we expect an efficacy of 40% reduction of inflammatory lesions (Gd-enhancing) and estimate that 30 patients will be required to detect a 40% reduction with a power of 0.8 and an alpha of 0.05 (one-sided). Sample size estimation is based on published statistical simulations (64).

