13.3.3 Clinical Safety Measures

The clinical measures are the changes in EDSS, SNRS, MSFC, and relapse rate. EDSS score will be obtained monthly as long as patients are treated with BOSWELAN either clinically or by telephone according to (62). The analyses will follow the same sequence of analyses as described for MRI. Comparison will always be made between baseline (week 0) and month 8 or earlier if treatment is stopped early.

14. Evaluation of Efficacy

Three efficacy populations will be analyzed for the primary outcome measures total Gd enhancing lesions and lesion volume:

The primary outcome in Stage 2 will first compare lesion (Gd-contrasting lesions) frequency (mean number of lesions) and area occurring during the 4 month baseline to lesion frequency and area occurring during months 5, 6, 7, 8 on treatment in patients treated with a dose of at least 800 mg t.i.d.

A secondary analysis will compare lesion frequency occurring over the 4 months of baseline to that occurring during over all treatment months.

An intention-to-treat analysis will be performed with all patients, all time on study.

Wilcoxon signed-rank test will be used for analysis of the primary endpoints.

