15. POTENTIAL RISKS / DISCOMFORTS AND BENEFITS TO PATIENTS

Direct benefits for single patients

BOSWELAN is an orally available anti-inflammatory drug that has a very good safety profile as has been already shown pre-clinically and in clinical studies (see 2.4 and 2.5). For patients that opt not to start on one of the established treatments of multiple sclerosis due to the mode of application by injection or infusion and/or fear of the side effect profiles of these treatments, BOSWELAN offers an alternative treatment. The study design without placebo allows treatment for all included patients. The study duration of up to 12 months makes it highly unlikely that if BOSWELAN shows no effect patients will have a substantial disadvantage through the delay for initiation of a licensed drug. A highly well tolerated drug for patients with only moderate to low disease activity is still missing. BOSWELAN might meet this unmet need.

Indirect benefits for clinical trial development in MS

We expect that BOSWELAN will decrease the average number of monthly contrast-enhancing MRI lesions by 40% or greater (primary outcome). While in established treatments in MS monitoring for dose finding and responder profiling is an issue of recent research, well known biomarkers for the pharmacodynamics of BAs activity (i.e. Cat G and PGE₂) exist, that can be useful for dose finding and responder profiling. With this study a putative highly effective clinical screening design for investigational drugs will be further developed. We aim at paralleling primary endpoint MRI analysis with mechanistic studies and further development of more disease-prognosis associated MRI markers.

Scientific benefits

BOSWELAN offers a new therapeutic approach through a new mode of anti-inflammatory action by single- and dual inhibition of three enzymes (Cat G, 5-LO and mPGES) that has so far not been looked at in the context of multiple sclerosis in spite of evidence for a role of these enzymes in neuroinflammation (see 2.2). The study will clarify the relevance of these mechanisms in MS/CIS.

Commitment of time

Monthly visits require approximately 3 hours a month, at first drug administration 2 further hours have to be spent at the study center.

Risks of MRI

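### The primary efficacy endpoint is defined in three incompatible ways (lesion number; number and volume; number and area), and the sample size supports only lesion number

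*Protocol*

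**What the plan says.** The current protocol text gives three definitions of the primary efficacy endpoint.

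- **Number only.** The Summary's statistical plan says that the primary outcome "will first compare mean Gd-enhancing lesion number occurring during the 4 month baseline to mean Gd-enhancing lesion number" on treatment. Section 2.3 (Stage 3) says "The primary outcome will assess the change in mean Gd-enhancing lesion number from the baseline". Section 15 expects that "BOSWELAN will decrease the average number of monthly contrast-enhancing MRI lesions by 40% or greater (primary outcome").
- **Number and volume.** The Summary's efficacy parameters list "Number and volume of total Gd-enhancing lesions" as the primary outcome measure. Section 3.2 says "The primary efficacy outcome measure of this study will be the mean total number and the volume of Gd-enhancing lesions". Section 14 opens with "Three efficacy populations will be analyzed for the primary outcome measures total Gd enhancing lesions and lesion volume".
- **Number and area.** The next sentence of section 14, which sets out the comparison of baseline with months 5 to 8, speaks of lesion frequency and area. Volume does not appear in it.

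Section 14 closes with "Wilcoxon signed-rank test will be used for analysis of the primary endpoints", in the plural. It gives no significance level, no order of testing, and no statement whether one or both endpoints must succeed.

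Section 13.1 estimates that 30 patients are needed to "detect a 40% reduction with a power of 0.8 and an alpha of 0.05 (one-sided"). The reduction is in Gd-enhancing lesions. No effect size or variance is given for volume or area. One-sided 0.05 is the only alpha in the protocol, and it appears only in the sample-size statements (Summary and section 13.1).

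**The concern.** The protocol does not merely leave a detail for the SAP. It fixes the endpoint several times, in ways that cannot all be true. Any SAP would have to depart from some section of the protocol to settle it.

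This matters because number and volume can disagree: a few large lesions may persist while the count falls, or the reverse. An author could then report either result as the pre-specified primary outcome and cite a protocol section in support. In a single-arm, open-label trial, naming the endpoint in advance is one of the few protections against choosing it after the data are seen. It also decides what the 30 patients are meant to deliver, because the stated 5% error and 80% power were set for one endpoint.

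**Working it through.** **Inputs.** From section 13.1: 30 patients, 40% reduction, power 0.80, one-sided alpha 0.05; also 12 patients for a 60% reduction at the same alpha (power not stated there, taken as 0.80). The protocol gives no lesion rate, variance, or correlation between number and volume, so the correlation r between the two test statistics is assumed and varied from 0 to 0.95.

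**Step 1: the plan's own figure.** With a paired normal approximation, n = ((z₀.₉₅ + z₀.₈₀) / d)², where d is the standardised paired effect and z₀.₉₅ + z₀.₈₀ = 1.645 + 0.842 = 2.486.

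- 30 patients imply d = 2.486/√30 = 0.454, so the SD of the relative change is 0.40/0.454 ≈ 0.88.
- 12 patients imply d = 2.486/√12 = 0.718, so the SD is 0.60/0.718 ≈ 0.84.
- Scaling 12 patients from 60% to 40% gives 12 × (0.6/0.4)² = 27 on the linear scale, or 12 × (ln 0.4/ln 0.6)² ≈ 39 on the log scale.

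So 30 is plausible, but it can be neither confirmed nor refuted without a variance. The cited source does not help: reference 64 in the list is a book on cultural history and botany, not a set of simulations.

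**Step 2: which endpoint was sized.** Section 13.1 speaks of a 40% reduction in enhancing lesions, and section 15 calls a 40% reduction in the average *number* of lesions the primary outcome. The sizing is therefore for the count.

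**Step 3: either endpoint suffices, each at one-sided 0.05.** Chance of at least one false positive = 0.05 + 0.05 − P(both statistics exceed 1.645), bivariate normal.

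**Step 4: both must succeed, each at 0.05.** Error when neither endpoint has an effect = P(both exceed 1.645). Power = P(both exceed 1.645) with each mean at 2.486, which assumes volume is as detectable as number.

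| r | Step 3: false-positive chance | Step 4: error, no effect on either | Step 4: power at 30 patients |
|---|---|---|---|
| 0 | 0.0975 | 0.0025 | 0.64 |
| 0.5 | 0.088 | 0.012 | 0.69 |
| 0.7 | 0.080 | 0.020 | 0.71 |
| 0.8 | 0.075 | 0.025 | 0.73 |
| 0.9 | 0.068 | 0.032 | 0.75 |
| 0.95 | 0.063 | 0.037 | 0.76 |

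With independent endpoints, power of 0.80 for both needs √0.80 = 0.894 on each: n = ((1.645 + 1.250)/0.454)² ≈ 40.7, so 41 patients.

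**Step 5: alpha halved to 0.025 each.** Power per endpoint = Φ(2.486 − 1.960) = 0.70. Restoring 0.80 needs n = ((1.960 + 0.842)/0.454)² ≈ 38.1, so 39 patients. The chance of success on at least one endpoint is 2 × 0.7007 − P(both succeed). That is 0.91 at r = 0, 0.81 at r = 0.7 and 0.74 at r = 0.95, again only if volume is as detectable as number.

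**Step 6: number as sole primary, volume tested only afterwards.** Alpha stays at one-sided 0.05, and power and sample size stay as stated.

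**The case against.** A reader might infer that the plan tests number and volume each at one-sided 0.05, so that its error rate exceeds 5%. The document does not say this. It attaches 0.05 to the sample size, not to either test in section 14, and it never says that success on one endpoint is enough. Section 3.2 uses the singular for number and volume together, which can equally mean that both are required; in that case error is not inflated. A rule on order, split or joint success may also sit in a SAP that is not shown, and its absence from the protocol is no fault. All of this stands, and the figures in step 3 are conditional for that reason.

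The size is open too. Number and volume of the same lesions are probably closely correlated, which favours the low end of the range, and the protocol gives no correlation. Halving alpha could still give at least an 80% chance of success on one endpoint or the other at correlations up to about 0.7, but only if volume is as detectable as number, which nothing in the protocol shows.

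The consequence is limited as well. The primary objective in section 3.1 is safety and tolerability, and its MRI safety parameter is clearly the mean total number of enhancing lesions. Efficacy comes second, in an open-label phase IIa study.

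None of this removes the contradiction among the sections, which no decision rule can resolve without changing some of them.

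**Conclusion.** The point holds as an inconsistency in the definition of the primary efficacy endpoint, in the current text. It does not hold as a claim that the trial's error rate exceeds 5%.

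No two-endpoint reading is shown to keep both stated figures:

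- **Either suffices at undivided 0.05:** false-positive chance of about 6.3% to 9.75% for assumed correlations from 0.95 down to 0.
- **Both required:** error stays within 5%, but power at 30 patients is about 0.64 to 0.76 across correlations 0 to 0.95.
- **Alpha halved:** power for lesion number, the endpoint that was sized, drops from 0.80 to about 0.70.

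The power figures rest on a normal approximation, on the effect implied by the stated 30 patients and, wherever both endpoints are involved, on volume being as detectable as number. Number as sole primary needs none of these assumptions to keep the plan's own figures. The change should be made, but the importance is moderate.

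**What to change.** Make mean Gd-enhancing lesion number, four baseline MRIs against months 5 to 8, the sole primary efficacy endpoint. This is what the Summary's statistical plan, section 2.3 and section 15 already say and what section 13.1 sizes. Test lesion volume next, at the same level, only if number is significant. In section 14, replace area by volume and make the primary endpoint singular. Align the Summary's outcome list, section 3.2 and the opening of section 14.

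The change is to wording only: 30 patients, one-sided 0.05 and power 0.8 all stay. The cost is that volume loses primary status. If the sponsor wants both endpoints to be primary, the protocol should state whether one or both must succeed, at what alpha, and the resulting power with an assumption for volume. On the assumptions above, that means about 39 patients for 0.80 per endpoint with alpha halved, or about 41 if both independent endpoints must succeed.
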